### **C 2 Withdrawal of informed consent for donated biological samples**

If a patient withdraws consent to the use of donated biological samples, the samples will be disposed of/destroyed, and the action documented. If samples are already analyzed, AstraZeneca is not obliged to destroy the results of this research.

Because collection of the biological sample(s) is an integral part of the study, the patient is withdrawn from further study participation.

The Principal Investigator ensures the following:

- Patients' withdrawal of informed consent to the use of donated samples is notified immediately to AstraZeneca.

- Biological samples from that patient, if stored at the study site, are immediately identified, disposed of/destroyed, and the action is documented.
- The organization(s) holding the samples is/are informed about the withdrawn consent immediately and that samples are disposed of/destroyed, the action is documented, and the signed document is returned to the study site
- The patient and AstraZeneca are informed about the sample disposal.

AstraZeneca ensures the organizations holding the samples are informed about the withdrawn consent immediately and that samples are disposed of/destroyed and the action is documented and returned to the study site.

### **C 3 International Airline Transportation Association (IATA) 6.2 Guidance Document**

#### **LABELLING AND SHIPMENT OF BIOHAZARD SAMPLES**

IATA classifies biohazardous agents into 3 categories

([http://www.iata.org/whatwedo/cargo/dangerous\\_goods/infectious\\_substances.htm](http://www.iata.org/whatwedo/cargo/dangerous_goods/infectious_substances.htm)). For transport purposes, the classification of infectious substances according to risk groups was removed from the Dangerous Goods Regulations in the 46th edition (2005).

Infectious substances are now classified as Category A, Category B, or Exempt. There is no direct relationship between Risk Groups and Categories A and B.

**Category A Infectious Substances** are infectious substances in a form that, when exposure to it occurs, is capable of causing permanent disability or life-threatening or fatal disease in otherwise healthy humans or animals. Category A pathogens (eg, Ebola, Lassa fever virus):

- Are to be packed and shipped in accordance with IATA Instruction 602.

**Category B Infectious Substances** are infectious substances that do not meet the criteria for inclusion in Category A. Category B pathogens include hepatitis A, B, C, D, and E viruses as well as human immunodeficiency virus types 1 and 2. They are assigned the following UN number and proper shipping name:

- UN 3373 – Biological Substance, Category B
- Are to be packed in accordance with UN3373 and IATA 650

**Exempt** includes all other materials with minimal risk of containing pathogens.

- Clinical trial samples will fall into Category B or exempt under IATA regulations.
- Clinical trial samples will routinely be packed and transported at ambient temperature in IATA 650 compliant packaging ([http://www.iata.org/whatwedo/cargo/dangerous\\_goods/infectious\\_substances.htm](http://www.iata.org/whatwedo/cargo/dangerous_goods/infectious_substances.htm)).
- Biological samples transported in dry ice require additional dangerous goods specification for the dry-ice content.
- IATA-compliant courier and packaging materials should be used for packing, and transportation and packing should be done by an IATA-certified person, as applicable.

Samples routinely transported by road or rail are subject to local regulations, which require that they are also packed and transported in a safe and appropriate way to contain any risk of infection or contamination by using approved couriers and packaging/containment materials at all times. The IATA 650 biological sample containment standards are encouraged wherever possible when road or rail transport is used.

## **Appendix D Genetics**

### **D 1 Use/analysis of DNA**

Genetic variation may impact a patient's response to therapy, susceptibility to, and severity and progression of disease. Variable response to therapy may be due to genetic determinants that impact drug absorption, distribution, metabolism, and excretion; MOA of the drug; disease etiology; and/or molecular subtype of the disease being treated. Therefore, where local regulations and IRB/IEC allow, a blood sample will be collected for DNA analysis from consenting patients.

AstraZeneca intends to collect and store DNA for genetic research to explore how genetic variations may affect clinical parameters, risk and prognosis of diseases, and the response to medications. Genetic research may lead to better understanding of diseases, better diagnosis of diseases, or other improvements in health care and to the discovery of new diagnostics, treatments, or medications.

In addition, collection of DNA samples from populations with well-described clinical characteristics may lead to improvements in the design and interpretation of clinical studies and, possibly, to genetically guided treatment strategies.

Genetic research may consist of the analysis of the structure of the patient's DNA, ie, the entire genome.

The results of genetic analyses may be reported in the CSR or in a separate study summary.

The Sponsor will store the DNA samples in a secure storage space with adequate measures to protect confidentiality.

The samples will be retained while research on durvalumab continues but no longer than 15 years or other period per local requirements.

### **D 2 Genetic research plan and procedures**

#### **Selection of genetic research population**

##### **Study selection record**

All patients will be asked to participate in this genetic research. Participation is voluntary, and if a patient declines to participate, there will be no penalty or loss of benefit. The patient will not be excluded from any aspect of the main study.

### **Inclusion criteria**

- For inclusion in this genetic research, patients must fulfil all of the inclusion criteria described in the main body of the Clinical Study Protocol **and** provide informed consent for the genetic sampling and analyses.

### **Exclusion criteria**

Exclusion from this genetic research may be for any of the exclusion criteria specified in the main study or any of the following:

- Previous allogeneic bone marrow transplant
- Non-leukocyte depleted whole blood transfusion in 120 days of genetic sample collection

### **Withdrawal of consent for genetic research**

Patients may withdraw from this genetic research at any time, independent of any decision concerning participation in other aspects of the main study. Voluntary withdrawal will not prejudice further treatment. Procedures for withdrawal are outlined in Section 7 of the main Clinical Study Protocol.

### **Collection of samples for genetic research**

The blood sample for genetic research will be obtained from the patients at the screening visit prior to randomization. Although DNA is stable, early sample collection is preferred to avoid introducing bias through excluding patients who may withdraw due to an AE; such patients would be important to include in any genetic analysis. If for any reason the sample is not drawn at the screening visit, it may be taken at any visit until the last study visit. Only 1 sample should be collected per patient for genetics during the study. Samples will be collected, labelled, stored, and shipped as detailed in the Laboratory Manual.

### **Coding and storage of DNA samples**

The processes adopted for the coding and storage of samples for genetic analysis are important to maintain patient confidentiality. Samples will be stored for a maximum of 15 years, from the date of last patient last visit, after which they will be destroyed. DNA is a finite resource that is used up during analyses. Samples will be stored and used until no further analyses are possible or the maximum storage time has been reached.

An additional second code will be assigned to the blood either before or at the time of DNA extraction replacing the information on the sample tube. Thereafter, the sample will be identifiable only by the second, unique number. This number is used to identify the sample and corresponding data at the AstraZeneca genetics laboratories or at the designated organization. No personal details identifying the individual will be available to any person (AstraZeneca employee or designated organizations working with the DNA).

The link between the patient enrollment/randomization code and the second number will be maintained and stored in a secure environment, with restricted access at AstraZeneca or designated organizations. The link will be used to identify the relevant DNA samples for analysis, facilitate correlation of genotypic results with clinical data, allow regulatory audit, and permit tracing of samples for destruction in the case of withdrawal of consent.

### **Ethical and regulatory requirements**

The principles for ethical and regulatory requirements for the study, including this genetics research component, are outlined in [Appendix A](#).

### **Informed consent**

The genetic component of this study is optional, and the patient may participate in other components of the main study without participating in the genetic component. To participate in the genetic component of the study, the patient must sign and date both the consent form for the main study and the genetic component of the study. Copies of both signed and dated consent forms must be given to the patient, and the original filed at the study center. The Principal Investigator(s) is responsible for ensuring that consent is given freely and that the patient understands that he/she may freely withdraw from the genetic aspect of the study at any time.

### **Patient data protection**

AstraZeneca will not provide individual genotype results to patients, any insurance company, any employer, their family members, general physician, unless required to do so by law.

Extra precautions are taken to preserve confidentiality and prevent genetic data being linked to the identity of the patient. In exceptional circumstances, however, certain individuals might see both the genetic data and the personal identifiers of a patient. For example, in the case of a medical emergency, an AstraZeneca Physician or an Investigator might know a patient's identity and also

have access to his/her genetic data. In addition, regulatory authorities may require access to the relevant files, although the patient's medical information and the genetic files would remain physically separate.

### **Data management**

Any genotype data generated in this study will be stored at a secure system at AstraZeneca and/or designated organizations to analyze the samples.

AstraZeneca and its designated organizations may share summary results (such as genetic differences from groups of individuals with a disease) from this genetic research with other researchers, such as hospitals, academic organizations, or health insurance companies. This can be done by placing the results in scientific databases, where they can be combined with the results of similar studies to learn even more about health and disease. The researchers can use this information only for health-related research purposes. Researchers may see summary results, but they will not be able to see individual patient data or any personal identifiers.

Some or all of the clinical datasets from the main study may be merged with the genetic data in a suitable secure environment separate from the clinical database.

### **Statistical methods and determination of sample size**

The number of patients who will agree to participate in the genetic research is unknown. It is therefore not possible to establish whether sufficient data will be collected to allow a formal statistical evaluation or whether only descriptive statistics will be generated. A Statistical Analysis Plan may be prepared where appropriate.

## **Appendix E Actions required in cases of increases in liver biochemistry and evaluation of Hy's law**

### **E 1 Introduction**

This appendix describes the process to be followed in order to identify and appropriately report cases of Hy's law. It is not intended to be a comprehensive guide to the management of elevated liver biochemistries. Specific guidance on managing liver abnormalities can be found in Dosing Modification and Toxicity Management Guidelines(for durvalumab).

During the course of the study, the Investigator will remain vigilant for increases in liver biochemistry. The Investigator is responsible for determining whether a patient meets potential Hy's law (PHL) criteria at any point during the study.

The Investigator participates, together with AstraZeneca clinical project representatives, in the review and assessment of cases meeting PHL criteria to agree whether Hy's law (HL) criteria are met. HL criteria are met if there is no alternative explanation for the elevations in liver biochemistry other than drug-induced liver injury (DILI) caused by the IP.

The Investigator is responsible for recording data pertaining to PHL/HL cases and for reporting AEs and SAEs according to the outcome of the review and assessment in line with standard safety reporting processes.

### **E 2 Definitions**

#### **Potential Hy's law (PHL)**

AST or ALT  $\geq 3 \times$  ULN **together with** TBL  $\geq 2 \times$  ULN at any point during the study following the start of study medication irrespective of an increase in alkaline phosphatase (ALP).

#### **Hy's law (HL)**

AST or ALT  $\geq 3 \times$  ULN **together with** TBL  $\geq 2 \times$  ULN, where no other reason, other than the IP, can be found to explain the combination of increases, eg, elevated ALP indicating cholestasis, viral hepatitis, or another drug.

For PHL and HL the elevation in transaminases must precede or be coincident with (ie, on the same day) the elevation in TBL, but there is no specified time frame within which the elevations in transaminases and TBL must occur.

### **E 3 Identification of potential Hy's law (PHL) cases**

In order to identify cases of PHL, it is important to perform a comprehensive review of laboratory data for any patient who meets any of the following identification criteria in isolation or in combination:

- ALT  $\geq 3 \times$  ULN
- AST  $\geq 3 \times$  ULN
- TBL  $\geq 2 \times$  ULN

When a patient meets any of the identification criteria, in isolation or in combination, the Investigator will:

- Notify the AstraZeneca representative
- Request a repeat of the test (new blood draw)
- Complete the appropriate unscheduled laboratory eCRF module(s) with the original local laboratory test result

When the identification criteria are met, the Investigator will without delay:

- Determine whether the patient meets PHL criteria (see [Appendix E, E 2](#) for definition) by reviewing laboratory reports from all previous visits

The Investigator will without delay review each new laboratory report and, if the identification criteria are met, will:

- Notify the AstraZeneca representative
- Determine whether the patient meets PHL criteria (see [Appendix E, E 2](#) for definition) by reviewing laboratory reports from all previous visits
- Promptly enter the laboratory data into the laboratory eCRF

## **E 4 Follow-up**

### **E 4.1 Potential Hy's law (PHL) criteria not met**

If the patient does not meet PHL criteria the Investigator will:

- Perform follow-up on subsequent laboratory results according to the guidance provided in the Clinical Study Protocol.

### **E 4.2 Potential Hy's law (PHL) criteria met**

If the patient does meet PHL criteria, the Investigator will:

- Notify the AstraZeneca representative who will then inform the central study team

The Study Physician contacts the Investigator, to provide guidance as well as discuss and agree on an approach for the study patients' follow-up and the continuous review of data. Subsequent to this contact, the Investigator will:

- Monitor the patient until liver biochemistry parameters and appropriate clinical symptoms and signs return to normal or baseline levels or as long as medically indicated
- Investigate the etiology of the event and perform diagnostic investigations as discussed with the Study Physician. This includes deciding which tests available in the Hy's law laboratory kit should be used
- Complete the 3 Liver eCRF Modules as information becomes available
- If at any time, in consultation with the Study Physician, the PHL case meets serious criteria, report it as an SAE using standard reporting procedures.

## **E 5 Review and assessment of potential Hy's law (PHL) cases**

The instructions in this section should be followed for all cases where PHL criteria are met.

No later than 3 weeks after the biochemistry abnormality was initially detected, the Study Physician contacts the Investigator in order to review available data and agree on whether there is an alternative explanation for meeting PHL criteria other than DILI caused by

the IP. The AstraZeneca Global Clinical Lead or equivalent and Global Safety Physician will also be involved in this review together with other subject matter experts as appropriate.

According to the outcome of the review and assessment, the Investigator will follow the instructions below.

If there is an agreed alternative explanation for the ALT or AST and TBL elevations, a determination of whether the alternative explanation is an AE will be made and subsequently whether the AE meets the criteria for an SAE:

- If the alternative explanation is **not** an AE, record the alternative explanation on the appropriate eCRF.
- If the alternative explanation is an AE/SAE, record the AE/SAE in the eCRF accordingly and follow the AZ standard processes.

If it is agreed that there is **no** explanation on the ALT or AST and TBL elevations other than the IP:

- Report an SAE (report term “Hy’s law”) according to AstraZeneca standard processes.
  - The “Medically Important” serious criterion should be used if no other serious criteria apply.
  - If there is no alternative explanation for the HL case, a causality assessment of “related” should be assigned.

If there is an unavoidable delay of over 3 weeks in obtaining the information necessary to assess whether or not the case meets the criteria for HL, then it is assumed that there is no alternative explanation until such time as an informed decision can be made:

- Report an SAE (report term “Potential Hy’s law”) applying serious criteria and causality assessment as per above.
- Continue follow-up and review according to agreed plan. Once the necessary supplementary information is obtained, repeat the review and assessment to determine whether HL criteria are met. Update the SAE report according to the outcome of the review amending the reported term if an alternative explanation for the liver biochemistry elevations is determined.

## **E 6 Actions required when potential Hy’s law (PHL) criteria are met before and after starting study treatment**

This section is applicable to patients with liver metastases who meet PHL criteria on study treatment having previously met PHL criteria at a study visit prior to starting study treatment.

At the first on-study treatment occurrence of PHL criteria being met, the Investigator will determine if there has been a significant change in the patients' condition# compared with the last visit where PHL criteria were met.#

- If there is no significant change, no action is required.
- If there is a significant change, notify the AstraZeneca representative, who will inform the central study team, then follow the subsequent process described in [Appendix B, B 5](#).
- # A “significant” change in the patient’s condition refers to a clinically relevant change in any of the individual liver biochemistry parameters (ALT, AST, or TBL), in isolation or in combination, or a clinically relevant change in associated symptoms. The determination of whether there has been a significant change will be at the discretion of the Investigator; this may be in consultation with the Study Physician if there is any uncertainty.

## **E 7      Actions required for repeat episodes of potential Hy’s law**

This section is applicable when a patient meets PHL criteria on study treatment and has already met PHL criteria at a previous on-study treatment visit.

The requirement to conduct follow-up, review, and assessment of a repeat occurrence(s) of PHL is based on the nature of the alternative cause identified for the previous occurrence.

The Investigator should determine the cause for the previous occurrence of PHL criteria being met and answer the following question:

Was the alternative cause for the previous occurrence of PHL criteria being met found to be the disease under study (eg, chronic or progressing malignant disease, severe infection or liver disease), or did the patient meet PHL criteria prior to starting study treatment and at first on-study treatment visit, as described in [Appendix E, E 6](#)?

If **no**, follow the process described in [Appendix E, E 4.1](#).

If **yes**, determine if there has been a significant change in the patient's condition compared with when PHL criteria were previously met.

If there is no significant change, no action is required.

If there is a significant change, follow the process described in [Appendix E, E 4](#).

A "significant" change in the patient's condition refers to a clinically relevant change in any of the individual liver biochemistry parameters (ALT, AST, or TBL), in isolation or in combination, or a clinically relevant change in associated symptoms. The determination of whether there has been a significant change will be at the discretion of the Investigator; this may be in consultation with the Study Physician if there is any uncertainty.

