### **B 5 Important medical event or medical treatment**

Medical and scientific judgment should be exercised in deciding whether a case is serious in situations where important medical events may not be immediately life threatening or result in death, hospitalization, disability, or incapacity but may jeopardize the patient or may require medical treatment to prevent one or more outcomes listed in the definition of serious. These should usually be considered as serious.

Simply stopping the suspect drug does not mean that it is an important medical event; medical judgment must be used.

- Angioedema not severe enough to require intubation but requiring IV hydrocortisone treatment
- Hepatotoxicity caused by paracetamol (acetaminophen) overdose requiring treatment with N-acetylcysteine
- Intensive treatment in an emergency room or at home for allergic bronchospasm

- Blood dyscrasias (eg, neutropenia or anemia requiring blood transfusion) or convulsions that do not result in hospitalization
- Development of drug dependency or drug abuse

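### Appendix E 7 sends some repeat potential Hy's law cases to the section for patients who do not meet the criteria, and E 6 points to a section with no liver process

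*Protocol*

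**What the plan says.** Appendix E sets out how PHL cases are found, followed up and assessed. E 4 has two parts. E 4.1, for patients who do not meet the criteria, contains one instruction: "Perform follow-up on subsequent laboratory results according to the guidance provided in the Clinical Study Protocol". E 4.2, for patients who do, starts with notifying the sponsor's representative, who informs the central study team. The Study Physician then agrees the follow-up with the investigator. Further steps include "Investigate the etiology of the event and perform diagnostic investigations as discussed with the Study Physician".

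E 7 deals with repeat episodes. It makes follow-up, review and assessment of a repeat "based on the nature of the alternative cause identified for the previous occurrence". It asks whether the earlier episode was due to the disease under study, or whether the patient met the criteria both before treatment and at the first on-treatment visit, as in E 6. If the answer is no, the investigator is to "follow the process described in [Appendix E, E 4.1". If it is yes and the patient's condition has changed significantly, E 4 as a whole applies. If it is yes without such a change, nothing more is required.

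E 6 concerns patients with liver metastases who met PHL criteria before treatment and meet them again on treatment. On a significant change the sponsor is notified, and the investigator is then to "follow the subsequent process described in [Appendix B, B 5". That section is headed "B 5 Important medical event or medical treatment".

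**The concern.** The no-branch of E 7 can be reached only by a patient who currently meets PHL criteria, yet it leads to the section written for patients who do not. The patients sent there are those whose earlier episode was not explained by the disease, including any whose earlier episode was attributed to study drug. Hy's law surveillance exists above all to catch these cases. A disease-explained repeat with a significant change is sent to the fuller E 4, so the intensity of follow-up runs the wrong way.

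The setting makes this relevant. Section 2.3.2.2 lists hepatitis and raised transaminases among the durvalumab risks, Section 8.3.13.1 lists hepatitis as an adverse event of special interest, and Sections 8.2.1 and 8.3.8 refer investigators to Appendix E for instructions.

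The E 6 reference is a smaller fault of the same kind: its target contains no process for a liver case.

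**Working it through.** No arithmetic applies beyond counting steps. Each reference was traced to its target, and the target was compared with the situation that triggers it.

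| Reference | Patient's situation | Target | What the target covers |
|---|---|---|---|
| E 7, answer no | PHL criteria met again; earlier episode not disease-related and not an E 6 case | E 4.1 | Criteria not met; laboratory follow-up only |
| E 7, answer yes, significant change | PHL criteria met again; earlier episode disease-related or an E 6 case | E 4 | Both parts, so E 4.2 for this patient |
| E 6, significant change | PHL criteria met before and on treatment; liver metastases | Appendix B 5 | Definition of an important medical event |

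**E 7.** The branch's own entry condition excludes its target. E 4.1 has 1 step. E 4.2 has 5 listed investigator actions plus Study Physician contact:

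1. Notify the sponsor's representative, who informs the central study team.
2. Monitor until liver tests and clinical signs return to normal or baseline, or for as long as medically indicated.
3. Investigate the cause, including a choice of tests from the Hy's law laboratory kit.
4. Complete the three liver modules of the case report form.
5. Report as a serious adverse event if serious criteria are met.

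**What survives elsewhere.**

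- Action 1, in part: E 3 says "The Investigator will without delay review each new laboratory report and, if the identification criteria are met, will" notify the sponsor's representative, check whether PHL criteria are met and enter the laboratory data. It does not mention the central study team.
- Action 5: Section 8.4.1 requires all serious adverse events to be reported.
- Action 3, in part: Section 8.4.5 asks in general terms that other causes be ruled out. It does not mention the Hy's law kit or agreement with the Study Physician.
- The follow-up plan agreed with the Study Physician and the three liver modules are not restored elsewhere.

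**E 5.** It opens with "The instructions in this section should be followed for all cases where PHL criteria are met" and contains the review of cause within 3 weeks. Taken alone, that would cover repeat cases. But E 7 makes review and assessment of repeats depend on its own question, and one of its branches ends with no action at all. That branch makes sense only if E 7 overrides the general rules for repeats, so an investigator following E 7 has some reason to doubt that E 5 applies automatically.

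**E 6.** The notification wording that precedes the faulty reference closely mirrors the first action in E 4.2. This suggests that the process meant to follow is the rest of E 4.2, with E 5.

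**Size of the E 6 group.** PHL needs total bilirubin of at least 2 times the upper limit of normal. Inclusion criterion 11 limits it to 1.5 times at entry, except in Gilbert's syndrome. A patient would have to meet the higher threshold before treatment and also have liver metastases, so the group is close to empty.

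**The case against.** The best defence is that the wrong reference exposes itself. E 4.1 is conditional on the criteria not being met, so its condition is false for every patient whom E 7 sends there. E 4.2 applies by its own terms to anyone who meets the criteria, and E 5 claims all such cases. The only explicit release in E 7 lies in the yes-branch, so nothing in the no-branch waives E 5. E 5 itself brings in the Study Physician and senior sponsor staff within 3 weeks. Appendix E also states that it is not the full guide to managing liver abnormalities; that guidance is in the separate toxicity management guidelines, which are not part of this document. On this view the point is editorial.

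Much of this stands. A careful reader can recover the intended path, and harm to a patient is not shown. The steps at risk are fewer than a bare comparison of one with five suggests. The exact target intended in E 6 is also a reconstruction, since Appendix B 5 could be a slip for Appendix E 5.

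It does not remove the fault. The investigator must disregard an explicit instruction to reach the right one, in a section that presents itself as the special rule for repeats. The agreed follow-up plan, the Hy's law kit work-up and the liver modules still depend on E 4.2.

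**Conclusion.** The point holds. Both cross-references are wrong in the current protocol text. The one in E 7 matters more, because it belongs to an operative safety rule and, read literally, gives less follow-up to repeat cases that the disease does not explain than to disease-explained repeats with a significant change. The text contradicts itself, but it does not make a bypass certain: sponsor notification and serious adverse event reporting are kept, and E 5 probably, though not clearly, still applies.

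Few patients are assumed to be affected; the protocol gives no expected rate of PHL or of repeat episodes. There is no effect on the endpoints, the type I error or the power. The correction should be made, but the study's conclusions do not depend on it.

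**What to change.** In Appendix E 7, replace the no-branch reference to E 4.1 with Appendix E, E 4.2, followed by E 5. In Appendix E 6, replace the reference to Appendix B 5 with Appendix E, E 4.2 and E 5.

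The cost is two corrected references, made in the next amendment or by an administrative letter to sites. Visits, data collection and analysis do not change.
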